### **7.5.5 Year 3 Efficacy**

The following binary endpoints are summarized by treatment regimen with response rates using NC = M at baseline and each scheduled visit on treatment through Week 144 for the Year 3 Efficacy Cohort (see [Section 6.3](#)):

- HBeAg loss
- HBeAg seroconversion
- HBsAg loss
- HBsAg seroconversion

The Year 3 Efficacy Cohort is defined for observed (NC = M) Week 48 HBeAg non-seroconverters by observed (NC = M) Week 96 HBeAg seroconversion status. Endpoints are summarized for ETV Week 96 non-seroconverters only through Week 96.

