4.1.1 Subject Management Decisions

Assessment of HBeAg seroconversion will be done, as needed, at Study Weeks:

- 52 (based upon Week 48 result);
- 100 (based upon Week 96 result); and
- 148 (based upon Week 144 result).

The investigators shall conduct the assessment of HBeAg response status at the assessment time points; this will be cross checked centrally by the BMS Medical Monitor/Protocol Manager. Subjects achieving HBeAg seroconversion shall initiate consolidation therapy for an additional 48 weeks as follows:

- At Week 52 (consolidation using blinded therapy to Week 96; 48 weeks counting from Week 48)
- At Week 100 (consolidation using open-label ETV to Week 144; 48 weeks counting from Week 96)
- At Week 148 (consolidation using open-label ETV to Week 192; 48 weeks counting from Week 144)

Subjects who achieve HBeAg seroconversion and revert back to HBeAg-positivity or develop HBeAg-negative CHB shall be managed as follows:

- Any subject who achieves HBeAg seroconversion by the Week 48 assessment and reverts to HBeAg-positive status before reaching Week 96 will be treated with open-label ETV until study Week 144, and then will stop study therapy and proceed to the LTFU phase;
- Any subject who achieves HBeAg seroconversion after the Week 48 assessment, who reverts back to HBeAg-positive status shall stop study treatment, if applicable, and be treated at the discretion of the investigator in consultation with the BMS Medical Monitor.
- Subjects who develop HBeAg-negative CHB (absence of HBeAg, presence of anti-HBe antibodies, active viral replication [HBV DNA by PCR assay $\geq 10,000$ copies/mL] and biochemical or histological evidence of hepatitis) shall be managed at the discretion of the investigator in consultation with the BMS Medical Monitor.

Study treatment (ETV and placebo) shall be provided during the blinded and open-label study treatment phases. Rescue open-label ETV shall be provided to subjects who experience extreme elevations of ALT due to acute exacerbations of CHB upon investigator request and approval by the Central Medical Monitor (see section 4.1.2).

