## 6 STUDY PERIODS, TREATMENT REGIMENS AND POPULATIONS FOR ANALYSES

### 6.1 Study Periods

Study periods for efficacy and safety analyses are defined as follows:

- **Pre-treatment period** begins at the first visit until initiation of study therapy.
- **On-treatment period** begins after the first day of study therapy and ends at the last dose of study therapy plus 5 days.
- **ETV treatment period** begins after the first day of active ETV and ends at the last dose of active ETV plus 5 days.
- **Off-treatment follow-up period** begins on the last dose of study therapy plus 6 days and ends at the start of alternative anti-HBV therapy minus 1 day.
- **Long-term follow-up period** begins on the last dose of study therapy plus 6 days until the end of the study.
- **Alternative ETV follow-up period** begins on the later of the last dose of study therapy plus 6 days and the start of alternative ETV therapy, until the end of the study.

Note that rescue open-label ETV is considered alternative anti-HBV therapy. See [Section 8.9](#) for additional conventions.

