### **7.5 Efficacy**

Efficacy endpoints are presented by as-randomized treatment regimen for treated subjects.

Binary efficacy endpoints are analyzed using 2 algorithms:

- Non-Completer = Failure (NC = F): The numerator is based on subjects meeting the response criteria. The denominator is based on treated subjects. Subjects who have missing data at the analysis week are considered as failures.
- Non-Completer = Missing (NC = M): The numerator is based on subjects meeting the response criteria. The denominator is based on subjects with data at the analysis week. Subjects who have missing data at the analysis week are excluded.

Treatment regimens are compared using a difference in proportions (ETV - PBO), 95% confidence interval (CI) and p-value based on  $NC = F$  for the primary endpoint and key secondary endpoints. Analyses are stratified by age randomization strata (see [Section 7.3.4](#)). The proportions are computed within each stratum, and combined using a weighted average with weights proportional to stratum size (Cochran-Mantel-Haenszel [CMH] weighting). ETV will be considered superior to PBO if the p-value is  $< 0.05$ . CIs for differences in proportions are based on the stratified normal approximation to the binomial distribution with unpooled proportions used in the computation of the standard error of the difference.

A two-stage testing procedure will be employed for testing the primary and key secondary endpoints using  $NC = F$ . In the first stage, the test for primary endpoint will be performed. Provided the test result of the primary endpoint is significant (p-value  $< 0.05$ ), the second stage tests of the key secondary endpoints will be conducted. Because the tests for the key secondary endpoints will be conducted sequentially only if the test for the primary endpoint is successful, significance levels will not be adjusted for the first stage testing. All tests for treatment comparison will be two-sided at a significance level of 0.05.

For binary composite endpoints involving several components (eg, primary efficacy endpoint), only subjects who meet the response criteria for all components are considered to be responders for the composite endpoint. In addition, subjects who meet the response criteria for some components but are missing other components are considered to be missing the composite endpoint.

See also [Sections 8.4 to 8.8](#) for additional conventions.

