### **7.5.4 Year 2 Efficacy**

The following binary endpoints are summarized by treatment regimen with response rates using NC = F and NC = M at baseline and each scheduled visit on treatment through Week 96 for the Year 2 Efficacy Cohort (see [Section 6.3](#)):

- HBV DNA < 50 IU/mL
- HBV DNA < 50 IU/mL and HBeAg seroconversion
- HBV DNA < 50 IU/mL and ALT normalization

- HBV DNA < LOQ
- HBV DNA < LLD
- HBV DNA < LOQ, LOQ - < 50, 50 - < 172, 172 - < 1,720, 1,720 - < 17,200 and  $\geq 17,200$  IU/mL
- ALT normalization
- HBeAg loss
- HBeAg seroconversion
- HBsAg loss
- HBsAg seroconversion

The Year 2 Efficacy Cohort is defined by as-randomized treatment regimen for all treated subjects and observed (NC = M) Week 48 HBeAg seroconversion status. Therefore, the analysis of HBeAg seroconversion addresses maintenance of HBeAg seroconversion at Week 96 for those who seroconverted at Week 48. Endpoints are summarized for PBO only through Week 48.

Key binary endpoints (e.g., HBV DNA < 50 IU/mL, ALT normalization, HBeAg seroconversion) at Week 96 are summarized by subgroups defined in [Section 7.5.1](#) using NC = F and NC = M for ETV subjects.

HBV DNA values and changes from baseline ( $\log_{10}$  IU/mL) are summarized by treatment regimen at baseline and each scheduled visit on treatment through Week 96 for the Year 2 Efficacy Cohort.

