### **7.5.6 Year 4 Efficacy**

The binary endpoints described in [Section 7.5.5](#) are summarized with response rates using NC = M at baseline and each scheduled visit on treatment through Week 192 for the Year 4 Efficacy Cohort (see [Section 6.3](#)), defined as PBO-randomized observed HBeAg non-seroconverters at both Weeks 48 and 96 who HBeAg seroconverted at Week 144 (NC = M).

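### Year 3 and Year 4 on-treatment HBeAg rates use NC = M only, so late seroconverters who revert and stop treatment drop out of later denominators and final-visit maintenance is overstated

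*SAP*

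**What the plan says.** **Algorithm.** SAP 7.5.5 presents HBeAg loss and seroconversion (and the HBsAg counterparts) using "NC = M at baseline and each scheduled visit on treatment through Week 144 for the Year 3 Efficacy Cohort". SAP 7.5.6 uses "NC = M at baseline and each scheduled visit on treatment through Week 192 for the Year 4 Efficacy Cohort". SAP 7.5 defines NC = M: "Subjects who have missing data at the analysis week are excluded". Year 2 differs: SAP 7.5.4 reports its endpoints "using NC = F and NC = M at baseline and each scheduled visit on treatment through Week 96".

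**Who is in the tables.** Under SAP 6.3, the Year 3 cohort is made up of Week 48 non-seroconverters, split by Week 96 status (S96 or NS96). The Year 4 cohort is placebo-randomised children who first meet the criterion at Week 144. Every S96 child and every Year 4 child is thus a late seroconverter.

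**What happens on reversion.** Protocol 4.1.1: "Any subject who achieves HBeAg seroconversion after the Week 48 assessment, who reverts back to HBeAg-positive status shall stop study treatment, if applicable". The rule for children who seroconverted by Week 48 is different. A child in that group who "reverts to HBeAg-positive status before reaching Week 96 will be treated with open-label ETV until study Week 144" stays observable on treatment.

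**Which data count as on treatment.** SAP 6.1: the period "begins after the first day of study therapy and ends at the last dose of study therapy plus 5 days". SAP 8.4 selects values within the study period before it applies visit windows.

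**The concern.** In these tables a child can leave the denominator because the child failed the endpoint being summarised. This is not ordinary missing data: the failure has been observed and recorded. No rule in SAP 7.5.5, 7.5.6 or 8.4 to 8.9 carries the reversion forward to later visits.

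The quantity a reader wants from the S96 and Year 4 tables is the share of late seroconverters who keep the response through the 48-week consolidation course. SAP 7.5.4 invites that reading, since it says the Year 2 seroconversion analysis addresses maintenance at Week 96. What the Year 3 and Year 4 tables give at their last visit is the share among children who had not already reverted and stopped. The two maintenance figures are also not comparable, because Week 48 seroconverters who revert remain on study ETV and stay in the on-treatment data.

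**Working it through.** The documents state no reversion rate and no expected Year 3 or Year 4 rate, so there is no plan figure to reproduce. The direction follows from the rules; the size needs assumptions.

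**Inputs from the documents**
- Serology is taken every 12 weeks on treatment (Protocol Table 6.1). Consolidation visits are Weeks 108, 120, 132 and 144 in Year 3, and Weeks 156, 168, 180 and 192 in Year 4.
- The Week 144 window is more than 138 and up to 150 weeks (SAP Table 8.4-1).
- On-treatment data end at last dose plus 5 days (SAP 6.1).

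**Assumed quantities**
- *r*: cumulative share of late seroconverters who revert during consolidation.
- *f*: share of reverters who have stopped, and so have no on-treatment value, by the last visit.
- For the main table: no other dropout, and no reverter regains seroconversion.

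**Formula.** Of N children, N(1 − r) keep the response, f·r·N have left, and (1 − f)·r·N still show an HBeAg-positive value at the last visit.
- Maintained rate = 1 − r.
- NC = M rate at the last visit = (1 − r)/(1 − f·r).
- Overstatement = (1 − r)·f·r/(1 − f·r), which is positive whenever 0 < r < 1 and f > 0.

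**Results** (NC = M rate, with overstatement in percentage points)

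| r | Maintained | f = 0.25 | f = 0.50 | f = 0.75 | f = 1.00 |
|---|---|---|---|---|---|
| 5% | 95% | 96.2% (1.2) | 97.4% (2.4) | 98.7% (3.7) | 100% (5.0) |
| 10% | 90% | 92.3% (2.3) | 94.7% (4.7) | 97.3% (7.3) | 100% (10.0) |
| 20% | 80% | 84.2% (4.2) | 88.9% (8.9) | 94.1% (14.1) | 100% (20.0) |
| 30% | 70% | 75.7% (5.7) | 82.4% (12.4) | 90.3% (20.3) | 100% (30.0) |

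The column f = 0.75 corresponds to reversions spread evenly over the four visits, with those found at the last visit still counted.

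**Visit by visit**, for 100 children with r = 20% and even spread: NC = M gives 95/100 = 95.0%, 90/95 = 94.7%, 85/90 = 94.4% and 80/85 = 94.1%. The maintained series is 95%, 90%, 85% and 80%.

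**Small-number example.** Of 20 S96 children, 2 revert and stop before Week 144 and 1 is found HBeAg-positive at Week 144. NC = M gives 17/18 = 94.4%; with reverters kept as failures the rate is 17/20 = 85.0%.

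**Would plain NC = F do instead?** Take r = 10%, f = 0.75 and 10% other dropout, independent of reversion (10% per year is the dropout assumed in Protocol 8.1).
- NC = F: 0.90 × 0.90 = 81.0%, against a maintained rate of 90%.
- NC = M: 97.3%.
- Earlier reverters kept as failures, other missing excluded: 0.81/(0.90 × 0.925 + 0.075) = 0.81/0.9075 = 89.3%.

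The last rule comes closest to 90%.

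**The case against.** **NC = M is the protocol's own rule here.** Protocol 8.4.3 prescribes it for exploratory endpoints, and 8.3 calls those endpoints descriptive. Week 144 and Week 192 HBeAg rates are not among the primary, key secondary or other secondary endpoints in SAP 4.1 to 4.3. Week 96 HBeAg loss, seroconversion and maintenance are in SAP 4.3, which may explain why Year 2 has both algorithms. This stands, and it limits the importance. It does not remove the outcome-dependent exclusion.

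**The loss is visible.** SAP 7.1 allows proportions to be shown over the number evaluable, and S96 is 100% at Week 96 by construction, so a careful reader could divide by the starting number. That is plain NC = F, which mixes reverters with unrelated dropout.

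**Some reverters will still be counted at the last visit.** Table 6.1 requires serology at end of treatment. A child who stops a little over 6 weeks after Week 132 has that value in the Week 144 window. This stands; it lowers *f* and is why a range is shown.

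**Stronger readings a reader might infer, which the documents do not support:**
- *That a stated durability objective is compromised.* Protocol 2.2 and SAP 3.2 refer to durability off treatment; these are on-treatment tables.
- *That reversions vanish from the report.* The end-of-dosing row in SAP 7.5.8 shows a reverter as a non-responder, provided the child has off-treatment follow-up data. It is not split by S96 or Year 4 group, and the sustained-response analysis in 7.5.2.5 requires seroconversion at end of dosing, so neither replaces the missing rate.
- *That the final rates would be near 100% however many revert.* At r = 30% with even spread, the rate is 90.3%.
- *That the PBO NS96 Week 144 rate is inflated too.* That depends on whether the stopping rule covers seroconversion arising between the assessment weeks, which Protocol 4.1.1 does not say. ETV NS96 is summarised only through Week 96.

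**Conclusion.** The point holds for HBeAg loss and HBeAg seroconversion in ETV S96 and PBO S96 (through Week 144) and in the Year 4 cohort (through Week 192). The error lies at visits after the one that shows reversion, chiefly the final visit, and it is upward whenever any reverter has stopped before then.

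The size cannot be determined from the documents. Over f = 0.25 to 1.00, it is about 2 to 10 points if 10% revert and about 4 to 20 points if 20% revert. These figures assume no other dropout and no regained seroconversion.

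The consequence is confined to descriptive tables with no hypothesis test. The Week 48 primary and key secondary results are unaffected. The change is still worth making, because the tables will be read as maintenance rates.

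**What to change.** In SAP 7.5.5 and 7.5.6, for HBeAg loss and HBeAg seroconversion:
- Keep the NC = M rate.
- Beside it, add a rate in which a child who stopped study treatment after HBeAg reversion stays in the denominator as a non-responder at every later scheduled visit, through Week 144 (Year 3) or Week 192 (Year 4). Handle all other missing data as NC = M.
- Report the number of such reverters in each group.
- State whether an indeterminate HBeAg result, which SAP 8.8 imputes as positive, counts as reversion, and how children in PBO NS96 who seroconvert between assessment weeks are classified.

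Consider the same addition in SAP 7.5.7, which also uses NC = M only.

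The cost is SAP wording, one derivation rule and extra table rows. No new data are needed, because the reverting serology result and the end of treatment are already recorded. The added rates will look less favourable than NC = M. No change to the protocol's treatment rule is proposed.

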### **7.5.6 Year 4 Efficacy**

The binary endpoints described in [Section 7.5.5](#) are summarized with response rates using NC = M at baseline and each scheduled visit on treatment through Week 192 for the Year 4 Efficacy Cohort (see [Section 6.3](#)), defined as PBO-randomized observed HBeAg non-seroconverters at both Weeks 48 and 96 who HBeAg seroconverted at Week 144 (NC = M).

### **7.5.7 All ETV On-Treatment Efficacy**

The following binary endpoints are summarized with response rates using NC = M at baseline and each scheduled visit on ETV treatment through Week 144 for the All ETV Efficacy Cohort (see [Sections 6.3](#) and [8.4](#)):

- HBV DNA < 50 IU/mL
- HBV DNA < 50 IU/mL and HBeAg seroconversion
- HBV DNA < 50 IU/mL and ALT normalization
- HBV DNA < LOQ
- HBV DNA < LLD
- HBV DNA < LOQ, LOQ - < 50, 50 - < 172, 172 - < 1,720, 1,720 - < 17,200 and  $\geq 17,200$  IU/mL
- ALT normalization
- HBeAg loss
- HBeAg seroconversion
- HBsAg loss
- HBsAg seroconversion

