4 INVESTIGATIONAL PLAN

4.1 Study Design and Duration

[figure not shown]
This is a comparative, randomized, double-blinded, placebo-control, multicenter study, assessing the efficacy and safety of oral ETV in pediatric subjects with chronic HBV infection who are HBeAg-positive and nucleos[t]ide naive (< 12 weeks of prior therapy with any nucleos[t]ide antiviral agent with activity against hepatitis B virus). Chronic HBV-infected children and adolescents from 2 to < 18 years of age will be enrolled. Approximately 180 subjects will be randomized 2:1 to ETV or placebo (PLB) for a maximum of 96 weeks of blinded therapy, with the analysis of the primary endpoint at Week 48 to be conducted for the first 123 treated subjects. The randomization will be stratified by age group (2 to ≤ 6 yrs; > 6 to ≤ 12 yrs; > 12 to < 18 yrs). To ensure adequate representation, the target enrollment will be 30 subjects for each age group, with a minimum requirement of 18 subjects. At Week 52 an assessment of HBeAg seroconversion shall be performed based on Week 48 serology results. At the Week 52 assessment, all subjects who achieve HBeAg seroconversion will remain on blinded therapy through Week 96; subjects without HBeAg seroconversion will be switched to open-label ETV. Thereafter, assessment of HBeAg seroconversion shall be conducted at study Weeks 100 and 148 during the open-label treatment. Study subjects who achieve HBeAg seroconversion during open-label ETV at the respective assessment time points shall receive up to an additional 48 weeks of study treatment for consolidation. Open-label ETV may therefore be continued up to Week 144 in ETV

randomized subjects and Week 192 for placebo randomized subjects. All randomized study subjects who do not achieve HBeAg seroconversion will receive a maximum of 96 weeks of study ETV therapy (Figure 4.1).

After completing the blinded treatment or the open-label phase, all subjects will be followed in an observational long-term follow up (LTFU) phase until they complete a total of 5 years of study participation from the start of blinded treatment.

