- **Year 2 Efficacy Cohort** is treated subjects grouped as-randomized and according to observed Week 48 seroconversion status: ETV, PBO, ETV S48, PBO S48, ETV NS48 and PBO NS48 (S = seroconverter; NS = non-seroconverter). All treated subjects are included in ETV and PBO.
  - **Year 2 Primary Efficacy Cohort** is treated subjects in both Primary and Year 2 Efficacy Cohorts.
- **Year 3 Efficacy Cohort** is observed Week 48 non-seroconverters grouped as-randomized according to observed Week 96 seroconversion status: ETV S96, ETV NS96, PBO S96 and PBO NS96.
- **Year 4 Efficacy Cohort** is PBO-randomized observed non-seroconverters at both Weeks 48 and 96 who seroconverted at Week 144.
- **All ETV Efficacy Cohort** is treated as-randomized ETV subjects and PBO-randomized subjects who received open-label ETV.
- **Post-Year 1 Efficacy Cohort** is treated subjects grouped as-randomized: ETV, PBO, PBO subjects who only received blinded PBO (PBO BL), PBO subjects who received open-label ETV (PBO OL), and All ETV (ETV and PBO OL combined; see previous bullet).
- **Year 2 Safety Cohort** is treated subjects grouped as-treated: ETV, PBO subjects who only received blinded PBO (PBO BL), and PBO subjects who received open-label ETV (PBO OL). In addition, subjects must have received open-label ETV or > 54 weeks of study therapy (the upper bound of the Week 48 visit window; see [Sections 7.4.1](#) and [8.4](#)).
- **All ETV Safety Cohort** is as-treated ETV subjects and as-treated PBO subjects who received open-label ETV.
- **Post-Year 1 Safety Cohort** is treated subjects grouped as-treated: ETV, PBO, PBO subjects who only received blinded PBO (PBO BL), PBO subjects who received open-label ETV (PBO OL), and All ETV (ETV and PBO OL combined; see previous bullet).

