### 8.4 Visit Week Windows

For longitudinal presentations, values are first selected within their respective study periods (see Section 6.1). Next, windows around scheduled measurement times are constructed based on the midpoint between scheduled measurement visits and the value closest to the scheduled visit for each measurement is selected from those that fall within the window.

Visit windows are defined in Table 8.4-1:

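### The pooled All ETV response rates after ETV Week 96 (SAP 7.5.7) are selected by HBeAg response, so the HBeAg series cannot be read as the effect of a third year of entecavir

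*SAP*

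**What the plan says.** - **Cohort.** SAP 6.3: the All ETV Efficacy Cohort "is treated as-randomized ETV subjects and PBO-randomized subjects who received open-label ETV".
- **Series.** SAP 7.5.7 gives eleven binary endpoints (HBV DNA, ALT, HBeAg, HBsAg and combinations) as "response rates using NC = M at baseline and each scheduled visit on ETV treatment through Week 144".
- **NC = M.** SAP 7.5: "The denominator is based on subjects with data at the analysis week. Subjects who have missing data at the analysis week are excluded".
- **On-drug values only.** The ETV treatment period "begins after the first day of active ETV and ends at the last dose of active ETV plus 5 days" (SAP 6.1). Under SAP 8.4, "values are first selected within their respective study periods", so a value taken after stopping cannot fill a later on-ETV visit.
- **Treatment length.** Protocol 4.1: "All randomized study subjects who do not achieve HBeAg seroconversion will receive a maximum of 96 weeks of study ETV therapy". Under Protocol 4.1.1, Week 48 seroconverters consolidate on blinded drug to Week 96, Week 96 seroconverters on open-label drug to Week 144, and Week 144 seroconverters to Week 192. A Week 48 seroconverter who reverts before Week 96 receives open-label entecavir to Week 144. A child who seroconverts later and then reverts stops study treatment.
- **A neighbouring analysis.** SAP 7.5.5 makes a cut for this reason: "Endpoints are summarized for ETV Week 96 non-seroconverters only through Week 96". SAP 7.5.7 has no such cut, no split by reason for continuing, and no NC = F version.

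**The concern.** NC = M is usually chosen to set aside dropouts. Here it also removes children who reached a planned end of treatment, and that end is set by the HBeAg result, which is itself one of the outcomes tabulated. Two large groups leave at about ETV Week 96: persistent non-seroconverters, and Week 48 seroconverters who held their response. Those who stay are mostly children kept on drug because they had just seroconverted.

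A reader following the HBeAg rows from Week 96 to Week 144 would see a jump and could credit it to longer treatment. The secondary objectives include serologic response, so the table is likely to be read in that way.

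**Working it through.** **1. Last scheduled ETV week by path** (Protocol 4.1 and 4.1.1; placebo-arm children start open-label drug at study Week 52)

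| Path | Drug stops, study week | Last ETV week |
|---|---|---|
| ETV arm, seroconverted Week 48, held | 96 | 96 |
| ETV arm, no seroconversion by Week 96 | 96-100 | 96-100 |
| ETV arm, first seroconverted Week 96 | 144 | **144** |
| ETV arm, seroconverted Week 48, reverted before Week 96 | 144 | **144** |
| Placebo arm, first seroconverted Week 96 | 144 | 144 - 52 = 92 |
| Placebo arm, no seroconversion by Week 144 | 148 | 148 - 52 = 96 |
| Placebo arm, first seroconverted Week 144 | 192 | 192 - 52 = **140** |

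**2. Can a non-seroconverter reach the Week 108 window?** The window opens after 102 weeks (SAP Table 8.4-1). The Week 52, 100 and 148 visits have a tolerance of 10 days, and the ETV period adds 5 days.
- ETV arm: 100 + 10/7 + 5/7 = 102.1 weeks, a margin of one day.
- Placebo arm: 96 + 20/7 + 5/7 = 99.6 weeks.

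Non-seroconverters are therefore essentially absent from Week 108 on. This step needs no assumed rate.

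**3. The plan's own attrition figures.** SAP 7.5.7 states no expected rate. Protocol 8.1 does trace placebo children: 20 × 0.9 = 18; 18 × 0.9 = 16.2, given as 16; 16 × 0.9 = 14.4, given as 14. These reproduce, and the same convention is used below (10% yearly dropout, 10% placebo seroconversion, 120 and 60 randomised).

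**4. Denominator at ETV Week 96.** 120 × 0.9² + (60 × 0.9 × 0.9) × 0.9² = 97.2 + 39.4 = 136.6, about 137. This uses the plan's inputs only. Ever exposed to ETV: 120 + 48.6 = 168.6.

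**5. A central scenario.** Assumed, not in the documents: seroconversion in the first ETV year *s* = 25%, new seroconversion at the next assessment *q* = 20%, reversion among ETV-arm Week 48 seroconverters *r* = 10%.
- ETV arm at Week 96: 97.2 × 0.25 = 24.3 early seroconverters, of whom 2.43 have reverted; 72.9 others, of whom 14.58 newly seroconvert.
- Placebo arm: 43.74 at study Week 96, of whom 10.94 seroconvert and 9.84 remain a year later; 43.74 × 0.75 × 0.9 = 29.52 others, of whom 5.90 seroconvert at study Week 144 (ETV Week 92, inside the Week 96 window).
- Rate at ETV Week 96: (24.3 - 2.43 + 14.58 + 9.84 + 5.90) / 136.6 = 52.2 / 136.6 = 38%.
- Still on drug by the end of Weeks 108-144: late seroconverters (14.58 + 5.90) × 0.9 = 18.4; reverters 2.43 × 0.9 = 2.2; total 20.6.
- Rate: 18.4 / 20.6 = 89%. No drug effect after Week 96 has been assumed.

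**6. Ranges.** With *s* 20-25%, *q* 10-30% and *r* 0-20%, the ETV Week 96 rate is 25-47%. After it, 9-33 children remain (5-20% of those exposed), and 68-100% of them are late seroconverters.

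A lower corner takes *s* = 30%, *q* = 10%, *r* = 15%, with only 85% of late seroconverters holding their response.
- Late seroconverters: (68.04 × 0.10 + 27.56 × 0.10) × 0.9 = 8.60. Reverters: 29.16 × 0.15 × 0.9 = 3.94.
- If those who lose response stay in the denominator: 8.60 × 0.85 / 12.54 = 58%.
- If they stop, as Protocol 4.1.1 directs: 7.31 / (7.31 + 3.94) = 65%.

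**7. Direction under heavy reversion.** With *s* = 25%, *q* = 10% and *r* = 50%, the rate still goes from 32.2 / 136.6 = 24% to 10.24 / (10.24 + 12.15) = 46%.

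**The case against.** **Much of this is shown elsewhere.** SAP 7.5.5 presents Week 96 seroconverters separately to Week 144, SAP 7.5.6 presents placebo-arm Week 144 seroconverters to Week 192, and SAP 7.5.8 gives end-of-dosing rates for off-treatment follow-up subjects and splits its response shifts by ETV duration at 102 weeks. This stands for HBeAg and HBsAg, so it would be wrong to infer that the SAP overlooks the issue throughout. It does not correct the pooled series, and SAP 7.5.5 and 7.5.6 do not cover HBV DNA or ALT.

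**The table is descriptive.** This also stands. It carries no test, no ETV Week 144 rate appears among the legible endpoints, and Protocol 8.4.3 prescribes NC = M for exploratory endpoints. A reader might infer that the secondary objectives would be answered wrongly. The documents do not support that: the tested comparisons lie elsewhere, and the risk is confined to how this series is read.

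**Denominators may be displayed.** SAP 7.1 allows number with event over number evaluable, and leaves formats to a Data Presentation Plan that is not available here. A fall from about 137 to a few dozen or fewer would show attrition. It would not show that continuation depended on response.

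**Not only responders remain.** Reverters stay on drug, and stable early responders leave. Both are correct, so saying that only seroconverters remain would go too far.

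**HBV DNA and ALT.** A reader might expect these to climb too. Continuation is decided on HBeAg serology, and children with suppressed DNA but no seroconversion also leave at about Week 96. The documents do not settle the direction.

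**Conclusion.** The point holds as a selection artefact in one descriptive analysis. From ETV Week 108 on, the pooled NC = M rates describe late seroconverters plus some Week 48 reverters, and the HBeAg rates will rise because of who is still on drug. The mechanism follows from the treatment rules and the analysis conventions alone.

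The size does not. It rests on conversion, maintenance and reversion rates that are absent from the documents; the planning figure of 20% is for the composite endpoint, not for seroconversion. Under the assumed ranges, observed seroconversion goes from roughly 25-47% of about 137 children to roughly 60-100% of about 9-33. The upper part of that range fits the protocol better, because late seroconverters who revert are to stop treatment. The primary and key secondary results are unaffected.

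**What to change.** In SAP 7.5.7:

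1. End the pooled All ETV NC = M series at ETV Week 96, in line with the cut already made in SAP 7.5.5.
2. Show ETV Weeks 108-144 in a separate block by reason for continuing: consolidation in late seroconverters (Week 96 in the entecavir arm, Week 144 in the placebo arm), and Week 48 seroconverters who reverted.
3. Print the denominator at every visit, with a note that continuation past about 96 weeks depended on HBeAg response.

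As an optional companion, add a whole-cohort summary of the last on-ETV value, or a cumulative proportion ever responding with the full cohort as denominator. The cumulative version counts transient responses and should say so.

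The cost is a change of SAP wording and one more table block. No new data are needed and treatment is untouched. The downside is that there would be no pooled Week 144 rate.
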